3.1.5 Disease Evaluation Visits

Patients with worsening disease, as determined by the investigator, should return to the clinic as soon as possible for a disease evaluation visit. The investigator may also schedule a disease evaluation visit to determine if a patient has achieved clinical remission. Patients with UC will undergo a flexible sigmoidoscopy and MCS evaluation at the disease evaluation visit. Patients with CD will undergo an ileocolonoscopy and CDAI evaluation, with one exception: Patients who experience worsening disease while receiving efmarodocokin alfa will not undergo an ileocolonoscopy unless the visit corresponds to a time when an ileocolonoscopy is already scheduled to occur.

After determination of the patient's disease status, the investigator may initiate or discontinue treatment with efmarodocokin alfa as appropriate (see efmarodocokin alfa treatment algorithm in [Table 2](#)).

3.1.6 Safety Follow-Up Visit and Early Termination Visit

Patients will undergo safety follow-up or early termination assessments as outlined below:

- Patients who receive at least one dose of efmarodocokin alfa must undergo safety follow-up assessments 8 weeks after their final dose of study drug.

Patients who discontinue the study prematurely (prior to Week 104) and have received at least one dose of efmarodocokin alfa should return to the clinic for an early termination visit within 1 week. Patients who discontinue prematurely without having undergone at least 8 weeks of follow-up (observation) after their final dose of efmarodocokin alfa should also return to the clinic for a safety follow-up visit 8 weeks after their final dose.

Patients who are unwilling to complete the safety follow-up visit should return to the clinic for an early termination visit no later than 30 days after their final dose.

- Patients who discontinue the study prematurely (prior to Week 104) and have not received efmarodocokin alfa should return to the clinic for an early termination visit within 30 days. Follow-up assessments are not required for patients who discontinue the study at Week 104 without having received efmarodocokin alfa.

For patients who complete Week 52 and safety follow-up assessments prior to the implementation of Protocol Version 6 and re-enter the study, safety follow-up is to be repeated for Year 2, as outlined above. Details regarding assessments at the safety follow-up visit and the early termination visit are provided in [Appendix 1](#).

Patients who permanently discontinue study drug can receive rescue therapy at the investigator's discretion.

3.1.7 Corticosteroids

For patients on concomitant oral corticosteroids, the corticosteroid dose should be tapered until discontinuation. The corticosteroid tapering schedule may be at the discretion of the investigator. For patients who receive a course of efmarodocokin alfa 60 µg/kg IV Q4W, tapering should be initiated once the patient is stable, based on the investigator's judgment. Patients who cannot tolerate up to two corticosteroid taper attempts without experiencing recurrence of IBD symptoms or symptoms of corticosteroid withdrawal will be discontinued from the study as outlined in Section [4.6.1](#). Any patient requiring corticosteroids above the baseline dose (with baseline defined as either the baseline dose in the parent study or the last dose prior to initiation of the most recent course of efmarodocokin alfa 60 µg/kg IV Q4W during the extension study, whichever dose is the most recent) should be discontinued from the study.

3.1.8 Internal Monitoring Committee

An Internal Monitoring Committee (IMC) will monitor data on safety, efficacy, and study conduct on an ongoing basis. The IMC consists of Sponsor representatives from Clinical Science, Drug Safety, Biostatistics, and Statistical Programming and Analysis, and may invite representatives from other functional areas (e.g., Clinical Pharmacology, Research) or external experts on an ad hoc basis. Sponsor representatives will not be involved in the conduct of the study or have any contact with study investigators or site staff.

The IMC will review cumulative unblinded data on a periodic basis as defined in the IMC Charter. The data will include, but will not be limited to, demographic data, adverse events data (including serious adverse events and adverse events of special interest), ECG data, and relevant laboratory data. In addition to reviews on a periodic basis, ad hoc reviews may be requested by the IMC or the Sponsor at any time to address potential safety concerns. An interim efficacy analysis for parent Study GA39925 will be performed by the IMC (see Protocol GA39925, Section 6.9).

After reviewing the data, the IMC may make recommendations such as the following:

- The trial will continue as planned.
- The trial will continue with a reduction in dose level.
- The trial will stop for safety reasons.
- Additional analyses will need to be performed.
- Enrollment will be held pending further safety evaluation.

The IMC may also provide recommendations for amending the protocol after consideration of all available data, including making further dose and duration adjustments to optimize benefit-risk. Final decisions will rest with the Sponsor's study team.

Any outcomes of these reviews that affect study conduct will be communicated in a timely manner to the investigators for notification of their respective Institutional Review Boards (IRBs)/Executive Committees (ECs). Biannual summaries of the conclusions and recommendations of the IMC will be sent to the IRBs/ECs.

A detailed description of the procedures, data flow, and meeting schedule of the IMC will be provided in the IMC Charter.

3.2 END OF STUDY AND LENGTH OF STUDY

Patients in this study will receive treatment or undergo observation for up to approximately 2 years. The end of the study is defined as the date when the last patient completes his or her final study visit.

3.3 RATIONALE FOR STUDY DESIGN

3.3.1 Rationale for Efmarodocokin Alfa Dose and Schedule

The dose regimen of efmarodocokin alfa 60 µg/kg IV Q4W was selected on the basis of an integrated analysis of the clinical, PK, and PD data from the completed Phase Ia study (GA29468) and data from the Phase Ib study (GA29469). The 60 µg/kg IV Q4W regimen would provide a preliminary assessment of the benefit-risk of a treat-to-remission strategy to help inform the Phase III studies. The 60 µg/kg Q4W regimen enables drug exposure within the tolerable exposure range to evaluate whether efmarodocokin alfa is safe and efficacious in patients with UC or CD.

The dose regimen tested in Study GA40209 is similar to the highest dose regimen tested in the Phase II parent study GA39925 (90 µg/kg IV Q4W in the first 8 weeks of treatment and 60 µg/kg IV Q8W during the 4-month maintenance phase). The benefit-risk profile of the 60 µg/kg IV Q4W regimen is anticipated to be similar to this regimen with a 33% lower C_{max} (60 µg/kg IV Q4W vs. 90 µg/kg IV Q8W, respectively) during the first 8 weeks, but 2 times higher exposure over the subsequent 4 months (60 µg/kg IV Q4W vs. 60 µg/kg IV Q8W, respectively). The dose regimen in Study GA40209 may be adjusted on the basis of emerging data from the parent study GA39925 as described above.

3.3.2 Rationale for Pharmacokinetic Sample Collection

This study will employ a sparse PK sampling schedule to allow for assessment of potential relationships between long-term drug exposure and the safety and efficacy of the study drug.

3.3.3 Rationale for Biomarker Assessments

Biomarkers will be assessed in stool and colonic tissue to demonstrate evidence of biologic activity of efmarodocokin alfa in patients with UC and CD. The relationship between stool and colonic tissue biomarkers and safety and immunogenicity endpoints may also be explored. The assessment of biomarkers may include, but not be limited to, measurement of DMBT1 in colonic tissue biopsies.

4. MATERIALS AND METHODS

4.1 PATIENTS

Up to approximately 320 patients with moderate to severe UC or CD from Study GA29469 or Study GA39925 will be enrolled in this study.

4.1.1 Inclusion Criteria

4.1.1.1 Inclusion Criteria for Study Entry

Patients must meet the following criteria for study entry:

- Prior enrollment in Study GA29469 or Study GA39925, with one of the following having occurred during that study:

Patients previously enrolled in Study GA29469

- Unable to achieve clinical response (defined for patients with UC and CD in Section 3.1.4.1) during the study and completion of the study through at least Day 85
- Initiation of protocol-defined rescue therapy during the study and completion of the study through at least Day 85
- Completion of the study through Day 134

Patients previously enrolled in Study GA39925

- Unable to achieve protocol-defined clinical response by Week 8
- Initiation of protocol-defined rescue therapy during the study and completion of the study through at least Week 8
- Protocol-defined disease flare after Week 8
- Completion of the study through Week 30

- Age 18–80 years, inclusive, at time of signing Informed Consent Form

4.1.1.2 Inclusion Criteria for Study Entry and Study Re-Entry

Patients must meet the following criteria for study entry and study re-entry:

- Signed Informed Consent Form (at time of initial entry and again at time of study re-entry)
- Ability to comply with requirements of the study, in the investigator's judgment
- For women of childbearing potential: agreement to remain abstinent (refrain from heterosexual intercourse) or use contraceptive methods with a failure rate of <1% per year during the treatment period and for 8 weeks after the final dose of study drug or 18 weeks after final dose of study drug from Study GA39925 (due to the possibility of receiving vedolizumab), whichever is longer

A woman is considered to be of childbearing potential if she is postmenarcheal, has not reached a postmenopausal state (≥ 12 continuous months of amenorrhea with no identified cause other than menopause), and has not undergone surgical sterilization (removal of ovaries and/or uterus).

Examples of contraceptive methods with a failure rate of <1% per year include bilateral tubal ligation, male sterilization, hormonal contraceptives that inhibit ovulation, hormone-releasing intrauterine devices, and copper intrauterine devices (recommendations related to contraception and pregnancy testing in clinical trials, Clinical Trial Facilitation Group, final version, dated 2014-09-15, Section 4.1).

The reliability of sexual abstinence should be evaluated in relation to the duration of the clinical trial and the preferred and usual lifestyle of the patient. Periodic abstinence (e.g., calendar, ovulation, symptothermal, or postovulation methods) and withdrawal are not acceptable methods of contraception.

- For men: agreement to remain abstinent (refrain from heterosexual intercourse) or use a condom, and agreement to refrain from donating sperm, as defined below:

With female partners of childbearing potential or pregnant female partners, men must remain abstinent or use a condom during the treatment period and for 8 weeks after the final dose of study drug or 18 weeks after final dose of study drug from Study GA39925, whichever is longer, to avoid exposing the embryo. Men must refrain from donating sperm during this same period.

The reliability of sexual abstinence should be evaluated in relation to the duration of the clinical trial and the preferred and usual lifestyle of the patient. Periodic abstinence (e.g., calendar, ovulation, symptothermal, or postovulation methods) and withdrawal are not acceptable methods of contraception.

4.1.2 Exclusion Criteria

4.1.2.1 Exclusion Criteria for Study Entry

Patients who meet any of the following criteria will be excluded from study entry:

- Withdrawal of consent from parent study
- Discontinuation of study drug as required by the parent study protocol
- Discontinuation of study drug and withdrawal from Study GA29469 prior to Day 85 or from Study GA39925 prior to Week 8
- Non-compliance in the parent study, specifically defined as missing scheduled visits or non-adherence with background medications and concomitant medications

4.1.2.2 Exclusion Criteria for Study Entry and Study Re-Entry

Patients who meet any of the following criteria will be excluded from study entry and study re-entry:

- Pregnant or breastfeeding, or intending to become pregnant during the study or within 8 weeks after the final dose of study drug or 18 weeks after final dose of study drug from Study GA39925 (due to the possibility of receiving vedolizumab), whichever is longer
- Any new malignancy since enrolling in the parent study
- Any new significant uncontrolled comorbidity, such as cardiac, pulmonary, renal, hepatic, endocrine, or GI disorders, since enrolling in the parent study
- Any new signs or symptoms of infection judged by the investigator to be clinically significant since enrolling in the parent study
- Use of cyclosporine, tacrolimus, sirolimus, or mycophenolate mofetil (MMF) since enrolling in the parent study
- Prior treatment with etrolizumab, natalizumab, efalizumab, or any other anti-integrin agents (other than vedolizumab)

- Use of IV corticosteroid or topical corticosteroid (i.e., enemas or suppositories) at the time of entry into this study
- Abnormal laboratory value recorded at the last visit in the parent study, as defined below:
 - Hemoglobin < 90 g/L (9 g/dL)
 - Serum creatinine > 1.5 × upper limit of normal (ULN)
 - ALT, AST, or ALP > 2.5 × ULN, total bilirubin > 1.5 × ULN, or presence of abnormalities in synthetic function tests judged to be clinically significant by the investigator

Patients with known Gilbert syndrome who have unconjugated hyperbilirubinemia will not be excluded.

 - Platelet count < 100 × 10⁹/L (100,000/µL)
 - ANC < 1.5 × 10⁹/L (1500/µL)
 - Absolute lymphocyte count < 0.5 × 10⁹/L (500/µL)

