3.1.3 Study Participation during Year 2

The duration of the study *has been* extended from 1 year to 2 years with the implementation of Protocol Version 6. Patients who completed the study through Week 52 (Year 1) prior to the implementation of Protocol Version 6 may *still* be eligible for an additional year of treatment and/or observation, provided that certain criteria are met, as outlined in [Table 4](#). Participation during Year 2 is not required for such patients, and those who do not participate will be considered to have completed the study per protocol, provided required safety follow-up assessments have been completed.

Table 3 Algorithm for Continued Study Participation during Year 2

Patient Disposition Status at Time of Implementation of Protocol Version 6	Action to Be Taken
Has not yet reached Week 52	
Patient will continue study treatment or observation through Week 104 per algorithm in Table 2.
Has completed Week 52 visit but has not yet completed required safety follow-up assessments	
Patient may resume study treatment or observation through Week 104 per algorithm in Table 2. If resuming study treatment, there must be a minimum of 2 weeks since the last dose of efmarodocokin alfa.^a
Has completed Week 52 visit and required safety follow-up assessments ^b	
Re-consent patient within 8 weeks of implementation of Protocol Version 6.Conduct study re-entry screening assessments (including endoscopy) over a 3-week period to confirm study eligibility per criteria outlined in Section 4.1 and evaluate disease status. Daily diary recording will be re-initiated to enable collection of patient-reported outcome data for MCS, CDAI, and PRO2 assessments (see Section 4.5.4).If eligible for study re-entry, patient will resume study treatment (within 1 week of establishing eligibility) or undergo observation through Week 104 per algorithm in Table 2.

CDAI=Crohn's Disease Activity Index; MCS=Mayo Clinic Score; PRO2=Patient-Reported Outcome-2.

^a If resuming study treatment, there will be no visit window deviation if there is a minimum of 2 weeks since the last dose of efmarodocokin alfa.

^b Also includes patients who have completed Week 52 visit but do not require safety follow-up assessments because they did not receive efmarodocokin alfa during the study.

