4.5 STUDY ASSESSMENTS

The schedule of activities to be performed during the study is provided in [Appendix 1](#). All activities must be performed and documented for each patient.

Data collected from the final visit of the parent study will serve as Study Week 0 (initial visit) data for the extension study. Procedures and assessments that were performed at the final visit of the parent study do not need to be repeated at Study Week 0, with the exception of the ADA sample. A baseline ADA sample should be collected at baseline (Study Week 0).

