Complete physical examination ⁿ	x											x						
Limited physical examination ^o			x	x	x					x	x		x					
ECG ^p	x	x	x ^p			x	x	x	x			x	x					
Hematology ^q and chemistry ^r	x		x	x	x					x		x	x					
Lipase, coagulation, and lipids ^s (fasting)	x		x	x		x	x	x	x			x	x					
CRP	x		x		x					x		x						

Efmarodocokin Alfa—Genentech, Inc.

97/Protocol GA40209, Version 7

Appendix 1

Schedule of Activities (cont.)

Activity	Baseline	Efmarodocokin Alfa-Specific Activities ^{b, c} (±5 days)			Q8W, When Not Undergoing Efmarodocokin Alfa-Specific Activities ^e (±1 week)	Ongoing Activities ^f				DE/ET Visit ^g	UV Visit ^h	Re-entry Screening (3 weeks) ⁱ	Safety FU ^j (±5 days)					
	Study Week	Treatment Initiation ^d	Q4W When Not in Clinical Remission	4 and 8 Weeks after Achieving Clinical Remission		Study Week (±2 weeks)												
	0 ^a					28	52	80	104									
Pregnancy test ^t	x		x	x	Q4W					x		x	x					
Urinalysis ^u	x			x						x		x	x					
PK sample ^v	x		x	x		x		x		x			x					
ADA sample ^w	x ^a		Q12W ^w	x		x		x		x			x					
Stool sample ^x	x		x			x	x	x	x	x		x						
Diary						x ^{i, y}												
Efmarodocokin alfa ^{c, z}		x ^d	x															
Annual colon surveillance colonoscopy with biopsy ^{aa}						x ^{bb}												
UC-Specific Activities																		
Flexible sigmoidoscopy with biopsy ^{aa}	x					x	x	x	x	x		x						
MCS (pMCS plus endoscopy) ^{cc}	x					x	x	x	x	x		x						
pMCS ^{dd}			x	x	x						x ^{ee}		x					

Appendix 1

Schedule of Activities (cont.)

Activity	Baseline	Efmarodocokin Alfa-Specific Activities ^{b, c} (±5 days)			Q8W, When Not Undergoing Efmarodocokin Alfa-Specific Activities ^e (±1 week)	Ongoing Activities ^f				DE/ET Visit ^g	UV Visit ^h	Re-entry Screening (3 weeks) ⁱ	Safety FU ^j (±5 days)					
	Study Week	Treatment Initiation ^d	Q4W When Not in Clinical Remission	4 and 8 Weeks after Achieving Clinical Remission		Study Week (±2 weeks)												
	0 ^a					28	52	80	104									
CD-Specific Activities																		
Ileocolonoscopy with biopsy ^{aa}	x					x	x	x	x	x		x						
CDAI (including PRO2)	x	x	x	x	x	x	x	x	x	x	x	x	x					
SES-CD	x		x			x	x	x	x	x	x	x						

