- ^d Treatment initiation (i.e., first visit of period in which patient receives efmarodocokin alfa) may coincide with the Study Week 0 (baseline) visit or a subsequent scheduled visit that confirms the patient is not in clinical remission. The first dose of efmarodocokin alfa in the extension study is to be administered no less than 2 weeks after the last dose of study drug in parent study. For patients who complete the Week 52 visit but have not yet completed required safety assessments prior to the implementation of Protocol Version 6 (see Section 3.1.3): If treatment is resumed (*follow “Q4W When Not in Clinical Remission” column*), there must be a minimum of 2 weeks since the last dose of efmarodocokin alfa. For patients who complete the Week 52 visit and (if required) safety follow-up assessments prior to the implementation of Protocol Version 6: If the patient qualifies for study re-entry and is not in clinical remission, efmarodocokin alfa must be given within 1 week of establishing eligibility (*follow “Q4W When Not in Clinical Remission” column*).
- ^e For patients who achieve clinical remission while receiving efmarodocokin alfa, Q8W visits begin 16 weeks after *achieving clinical remission*.
- ^f Additional activities to be performed in all patients.
- ^g Patients with worsening disease, as determined by the investigator, should return to the clinic as soon as possible for a disease evaluation visit. The investigator may also schedule a disease evaluation visit to determine if a patient has achieved clinical remission. Patients who discontinue study drug prematurely (prior to Week 104) for the reasons listed in Section 4.6.1 and have received at least one dose of efmarodocokin alfa should return to the clinic for an early termination visit within 1 week of the event and will then enter the safety follow-up period. Patients who are unwilling to complete the safety follow-up period should return to the clinic for an early termination visit no later than 30 days after their final dose. Patients who discontinue the study prematurely (prior to Week 104) and have not received efmarodocokin alfa should return to the clinic for an early termination visit within 30 days. Endoscopy at the early termination visit should be conducted if the investigator deems it necessary.

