- ^h An unscheduled visit represents a visit that is not specified by the protocol but is determined to be necessary by the investigator or Sponsor (e.g., for evaluation of an adverse event). The indicated assessments are required for an unscheduled visit. Other assessments are optional for an unscheduled visit, per investigator discretion.
- ⁱ Patients who complete Week 52 and (if required) safety follow-up assessments prior to the implementation of Protocol Version 6 and agree to participate during Year 2 will undergo re-entry screening over a 3-week period to confirm study eligibility per criteria outlined in Section 4.1 and evaluate disease status. Daily diary recording will be re-initiated during re-entry screening to enable collection of patient-reported outcome data for MCS, CDAI, and PRO2 assessments (see Section 4.5.5).
- ^j Patients who receive at least one dose of efmarodocokin alfa must undergo safety follow-up assessments 8 weeks after their final dose. Patients who discontinue prematurely without having undergone at least 8 weeks of follow-up (observation) after their final dose of efmarodocokin alfa should return to the clinic for a safety follow-up visit 8 weeks after their final dose. Patients who are unwilling to return the clinic for the safety follow-up visit should undergo assessments indicated for an early termination visit no later than 30 days after their final dose. For patients who complete Week 52 and safety follow-up assessments prior to the implementation of Protocol Version 6 and re-enter the study, safety follow-up is to be repeated for Year 2.
- ^k Patients who complete Week 52 and (if required) safety follow-up assessments prior to the implementation of Protocol Version 6 and agree to participate during Year 2 must be re-consented within 8 weeks of implementation of Protocol Version 6.

Appendix 1

Schedule of Activities (cont.)

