- ^q Hematology includes WBC count, RBC count, hemoglobin, hematocrit, platelet count, and differential count (neutrophils, eosinophils, basophils, monocytes, lymphocytes, and other cells).
- ^r Serum chemistry includes sodium, potassium, chloride, bicarbonate, glucose, BUN or urea, creatinine, total protein, albumin, phosphorus, calcium, total and direct bilirubin, alkaline phosphatase, ALT, AST, uric acid, and LDH.
- ^s Lipid panel includes cholesterol, LDL cholesterol, HDL cholesterol, and triglycerides. Patients must be fasting (no food or fluids other than water will be allowed for approximately 8 hours prior to the visit and until after sample collection).
- ^t For women of childbearing potential undergoing efmarodocokin alfa treatment, urine pregnancy tests will be performed monthly, at specified subsequent visits. For women of childbearing potential not undergoing efmarodocokin alfa treatment, urine pregnancy tests will be performed Q4W. If a urine pregnancy test is positive, it must be confirmed by a serum pregnancy test.
- ^u Urinalysis includes specific gravity, pH, blood, qualitative protein, ketones, glucose, bilirubin, nitrite, leukocyte esterase, color, and appearance. If urinalysis is abnormal, the same urine sample will be sent to the laboratory for microscopic analysis (sediment, WBCs, RBCs, casts, crystals, epithelial cells, and bacteria), culture, and sensitivity.
- ^v PK samples should be collected in patients with signs and symptoms of serious opportunistic infections or if the mean QTcF is >500 ms and/or >60 ms longer than the baseline (Study Week 0) value, if not already scheduled to be collected at that timepoint.

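### The numeric laboratory limits for study re-entry are read only at the last parent-study visit, so the re-entry screening results are not required to meet them

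*Combined protocol and SAP*

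**What the plan says.** Section 4.1.2.2 opens with "Patients who meet any of the following criteria will be excluded from study entry and study re-entry". Its laboratory bullet reads "Abnormal laboratory value recorded at the last visit in the parent study, as defined below" and then lists limits for haemoglobin, creatinine, ALT, AST, ALP, total bilirubin, platelets, neutrophils and lymphocytes. The synopsis has the same bullet under the same joint heading. Section 4.5 fixes the visit in time: "Data collected from the final visit of the parent study will serve as Study Week 0 (initial visit) data for the extension study". The one criterion specific to re-entry, in Section 4.1.2.3, concerns prohibited concomitant therapy and sets no laboratory limit.

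Re-entry is for patients who had finished Week 52 and any required safety follow-up before Protocol Version 6. For them, Section 3.1.3, Table 3 says: "Conduct study re-entry screening assessments (including endoscopy) over a 3-week period to confirm study eligibility". Appendix 1, footnote i, says that these patients "will undergo re-entry screening over a 3-week period to confirm study eligibility per criteria outlined in Section 4.1 and evaluate disease status". In the Appendix 1 schedule, the row "Hematology ^q and chemistry ^r" is marked in the re-entry screening column. Footnote d adds: "If the patient qualifies for study re-entry and is not in clinical remission, efmarodocokin alfa must be given within 1 week of establishing eligibility".

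**The concern.** The plan collects fresh laboratory results in order to confirm eligibility, but the numeric eligibility rule looks at a different and much older set of results. Taken literally, a returning patient whose platelets or neutrophils at re-entry screening are outside the protocol's own limits meets no numeric exclusion.

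Two things are at stake. The first is safety: Section 5.1 relies on the eligibility criteria to keep out patients at higher risk of clinically significant adverse events, and at re-entry the numeric part of that safeguard does nothing. The second is a consistent Year 2 population: some sites may follow the wording while others apply the limits to the fresh sample, so the same result could lead to different decisions.

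**Working it through.** The plan states no figure on this point to reproduce. The check sets the sections side by side and then works out the age of the governing value.

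**1. Can the criterion exclude anyone at re-entry?** Its input is the last parent-study visit. Every correctly enrolled patient was judged on that same input at first entry and passed. The input is fixed, so the answer at re-entry is the same whatever the new results show.

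**2. Are the limited analytes measured again?** The panel contents are in Appendix 1, footnotes q and r; the chemistry footnote includes "creatinine, total protein, albumin, phosphorus, calcium, total and direct bilirubin, alkaline phosphatase, ALT, AST, uric acid, and LDH".

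| Limit in Section 4.1.2.2 | Panel at re-entry screening | Limit applied to the re-entry value | Stand-alone numeric action in Table 4 |
|---|---|---|---|
| Haemoglobin | Haematology | No | No |
| Platelets | Haematology | No | No |
| Neutrophils | Haematology | No | No |
| Lymphocytes | Haematology | No | No |
| Creatinine | Chemistry | No | No |
| Total bilirubin | Chemistry | No | No (only combined with ALT or AST) |
| ALP | Chemistry | No | No |
| ALT | Chemistry | No | Yes |
| AST | Chemistry | No | Yes |

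Re-measured: 4 + 5 = 9 of 9. Tested against the re-entry value: 0 of 9. Stand-alone numeric action in Table 4: 2 of 9. The bullet's judgment-based limb on synthetic function is tied to the parent-study visit in the same way.

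**3. How old is the governing value?** Time is counted from Study Week 0, taken as the final parent-study visit. Appendix 1 gives windows of ±2 weeks for Week 52 and ±5 days for dosing and safety follow-up visits. Safety follow-up falls 8 weeks after the final dose.

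- Minimum (never dosed, or follow-up already complete by Week 52): 52 − 2 = 50 weeks; nominal 52 weeks.
- Last dose at Week 48: 48 + 8 = 56 weeks nominal. Earliest: (48 weeks − 5 days) + (8 weeks − 5 days) = 56 weeks − 10 days = 54.6 weeks.
- Last dose at Week 52: 52 + 8 = 60 weeks nominal. Earliest: 60 weeks − 10 days = 58.6 weeks.

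The last-dose weeks are assumptions, because the plan does not state when the final Year 1 dose falls. Any wait for Version 6, or for re-consent (allowed up to 8 weeks after its implementation), lengthens the interval.

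**The case against.** The strongest reply is that re-entry is not unguarded. Section 4.1.2.2 still excludes a newly arisen uncontrolled comorbidity or a clinically significant infection. Section 5.3.5.5 makes the investigator responsible for reviewing every laboratory finding, Section 4.6.1 requires treatment to stop for any condition judged to endanger the patient, and the Internal Monitoring Committee sees laboratory data periodically. Re-entrants on treatment also have haematology and chemistry at each Q4W visit. All of this is true, and nothing here implies that recent results go unseen. But these safeguards are judgment-based or operate once the patient is back in the study. The protocol put numeric limits in the same list as its judgment criteria, and only the numeric ones stop working at re-entry.

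A second reply is that these are entry limits, not limits for continued dosing. Table 4 continues study drug at ALT or AST above 3 and up to 5 × ULN, although entry is refused above 2.5 × ULN. Patients who continue or resume under the first two rows of Table 3 face no numeric re-test. This tempers the size of the risk. It does not explain why the plan names re-entry in the heading of the list and screens for eligibility under Section 4.1, yet leaves the new values out.

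Third, the group is narrow, its size is unknown, and the re-consent window may be largely over. With descriptive, pooled safety analyses and no hypothesis test, the analytic effect is modest. Differing site practice is a possibility, not an observation. These points bear on the weight of the concern and are accepted. Version 7 still says such patients may be eligible, so the wording remains live.

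**Conclusion.** The concern holds. As written, the numeric laboratory criterion has no effect at re-entry: nine of nine limited analytes are measured again and none of the limits is applied to the new value. The governing result is at least about 50 weeks old, and 54.6 to 60 weeks old if the last Year 1 dose was at Week 48 or Week 52 (assumed). What is missing is the numeric test, not the whole screen. Only patients who completed Week 52 and any required safety follow-up before Version 6 are affected; the documents do not give their number. Medical history and baseline conditions are recorded again at re-entry, which limits the chance that an existing abnormality is later read as new. The point should be corrected, but it does not threaten the study's main conclusions.

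**What to change.** Reconcile Section 4.1.2.2 and the synopsis with Table 3 and Appendix 1 by naming the visit whose results decide re-entry. The bullet could refer to values *from the last parent-study visit (study entry) or from re-entry screening (study re-entry)*. Leave every listed limit as it is.

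If the 8-week re-consent window has closed at every site, an amendment would change nothing. In that case, list in the study report the re-entrants whose re-entry screening values were outside the limits.

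The edit is one line in two places and uses samples already scheduled. Because it alters an eligibility criterion, it needs ethics committee and, where locally required, regulatory approval under Section 9.6, so it is best combined with another amendment. Some re-entrants may be screened out, which would slightly reduce Year 2 exposure data. In the same edit, it would help to say whether the corticosteroid bullet, which refers to the time of entry, also covers re-entry.
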